We plan to recruit 40 patients for this study, and each patient will receive a single injection in each eye. Most patients receiving bilateral injections receive both injections in a 1-2 week period (1 eye at day 0, and the second eye by day 14). This is the current standard period between intravitreal injections, and is used regardless of the form of local anesthesia delivered. Some patients receive bilateral injections during the same clinic visit. First eye treatment will be randomly assigned to one of the CA treatment groups and the other eye will be randomly assigned to SOC.

2.0 Study Design:

2.1 General Study Design:

Prospective, interventional pilot study.

2.1.1 Study Design Schematic:

2.2 Subject Selection:

2.2.1 General characteristics of the proposed subject population(s):

Patients age >18 years old with bilateral macular disease due to either exudative macular degeneration or diabetic retinopathy requiring bilateral IVT and who had at least one prior IVT. To be included in this study, patients must be able to give informed consent.

Patients with bilateral macular disease requiring bilateral IVT will enable us to compare the effectiveness of CA compared to SOC in terms of pain reduction, with each patient serving as their own control.

2.2.2 Anticipated Number of Research Subjects:

We anticipate recruiting and enrolling 40 patients to complete this study (10 for each CA group). We expect that all 40 patients will complete the study.

2.2.3 Inclusion Criteria:

Inclusion criteria: Patients age >18 years old with bilateral macular disease due to either exudative macular degeneration or diabetic retinopathy requiring bilateral IVT. Only patients with at least one previous IVT will be recruited. To be included in this study, patients must be able to give informed consent.

2.2.4 Exclusion Criteria:

Exclusion Criteria: Patients < 18 years of age. Patients with unilateral disease, or patients with bilateral disease who are not able to give informed consent. Patients with preexisting conjunctival, episcleral or scleral defects or disease will be excluded.

2.3 Study Procedures:

2.3.1 Screening Procedures:

Physician will verify the need for IVT prior to beginning the study.

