After obtaining written consent, the brow above the eye to receive intravitreal treatment will be marked. Next, one drop of proparacaine will be applied into the eye to at least 5 minutes before any additional steps. Once the patient is ready, another drop of proparacaine will be applied and the physician or his assistant will then swab the lids with betadine. The physician will place a lid speculum in the patient’s eye. A drop of betadine will be applied at the site of treatment. The physician or his assistant will then activate the CA device by pressing the main button. He or she will review the LED display to verify that the device is set to achieve the correct temperature and time setpoints depending on the arm of the study to which the patient is randomized. The physician will adjust the temperature and time set points using the main device button if they are not correctly entered. The physician will then verbally review the selected treatment temperature and time, after which he or she will activate the device to enable the device tip to reach the required temperature. Immediately prior to placing the device tip against the eye, the physician will press the activation switch, after which he or she will apply the device to the surface of the eye. When the timer sounds, he or she will remove the device from the surface of the eye. The device tip has markers on it that will leave a temporary indentation 3 and 4 mm from the limbus. Immediately before giving the injection, the physician will place a drop of betadine on the surface of the eye at the site marked for the injection and wait 20 seconds. The physician will then give the intravitreal injection.

The procedure for the patients receiving SOC will be similar to that described above. After obtaining written consent, the brow above the eye to receive intravitreal

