treatment will be marked. Next, one drop of proparacaine will be applied into the eye to receive at least 5 minutes before any additional steps. Once the patient is ready, another drop of proparacaine will be applied and the physician or his assistant will then swab the lids with betadine. The patient will then have lidocaine gel placed on the eye and left in place for a minimum of 3 minutes prior to IVT. The 3-minute waiting period is needed to allow the lidocaine gel to diffuse through the sclera. Following completion of numbing, the eyelids will be swabbed with betadine and the physician will place the lid speculum. The physician will use a caliper to measure 3 or 4 mm from the limbus of the eye, place a drop of betadine over this spot, wait 20 seconds and then administer the injection.

2.3.2.1 Allocation to Treatment:

Patients will be randomly assigned to 1 of the 4 CA treatment groups and the SOC arm. Patients will be randomized to have their first eye receive either CA or SOC.

2.3.2.2 Treatment Adherence/Study Compliance:

If a patient is does not require, or refuses, an injection in either eye, they will be removed from the study. Because IVT prevents blindness, the refusal of IVT is extremely rare. In addition, it is extremely rare for patient who have been determined to need IVT to have improvement in vision prior to IVT.

If patients withdraw from the study, we will plan to recruit additional patients to replace them.

2.3.3 **Follow-up Procedures:**

2.3.3.1 Procedures to Assess Efficacy:

Patients will record their subjective pain (pre-injection preparation pain, injection pain, and 24 hr post injection pain) using a visual analog scale (1 to 10, with 10 being severe pain and 1 being no pain). The study coordinator will call the patients within 4 hours after their injection to review their 4-hr post procedure pain scores with them. Patients will be asked to return in 24 hours for anterior segment examination and 24-hr post injection pain assessment. Patients treated on Friday will be asked to return on Saturday for their 24-hr post injection assessment.

2.3.3.2 Procedures to Assess Safety:

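### Section 2.3.2.1 randomises what the first eye receives, but nothing requires right or left to be fixed as the first eye before the allocation is known

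*Protocol*

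**What the plan says.** Section 2.3.2.1 contains the allocation rule in two sentences: "Patients will be randomly assigned to 1 of the 4 CA treatment groups and the SOC arm", followed by "Patients will be randomized to have their first eye receive either CA or SOC". Section 1.4 words it differently: "First eye treatment will be randomly assigned to one of the CA treatment groups and the other eye will be randomly assigned to SOC".

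On timing, section 1.4 describes the usual pattern as "1 eye at day 0, and the second eye by day 14", and adds: "Some patients receive bilateral injections during the same clinic visit". No section says how the first eye is determined, who determines it, or when it is recorded.

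The injection procedure in section 2.3.2 begins: "After obtaining written consent, the brow above the eye to receive intravitreal treatment will be marked". The physician or assistant later checks that the device is set to the "correct temperature and time setpoints depending on the arm of the study to which the patient is randomized". The inclusion criteria in section 2.2.3 state: "Only patients with at least one previous IVT will be recruited".

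Section 2.2.1 makes each patient his or her own control. The primary endpoint in section 2.4.1 is injection pain, rated by the patient from 1 to 10.

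**The concern.** Randomising the treatment of the first eye settles the sequence of CA and SOC. It settles which physical eye gets CA only if the first eye has already been named. If it has not, a person who knows that CA comes first can decide the CA eye by deciding which eye goes first. A site could do this and still follow section 2.3.2.1 to the letter.

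The primary contrast is between the two eyes of one patient. Pairing removes differences between patients but not a selective choice between eyes. The endpoints in section 2.4.1 include no pain score for each eye from before the study, so the listed data could neither reveal such a choice nor adjust for it. The CA versus SOC pain estimate is what would be exposed.

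**Working it through.** **Step 1: the plan's own figure.** Section 2.2.2 gives 10 patients in each CA group, and section 2.3.2.1 gives four groups: 4 × 10 = 40, which agrees with the stated 40. The protocol gives no effect size, SD or power, so there is no calculation to compare a bias against.

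**Step 2: is the eye fixed before the allocation is known?**

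| Question | What the protocol gives |
|---|---|
| What is randomised? | Treatment of the first eye (2.3.2.1) |
| How is the first eye defined? | Not stated |
| When is it recorded relative to randomisation? | Not stated; brow marking follows consent but is not placed before or after allocation (2.3.2) |
| Do treating staff know the arm? | Yes; they check and set the device for it (2.3.2) |
| Is the order of eyes open? | At a single visit no rule sets it; over two visits the schedule may set it (1.4) |
| Could a difference between eyes be known? | Possibly; one earlier injection per patient is required, not one per eye (2.2.3) |

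**Step 3: simple size of the shift.** Let f be the share of patients whose CA eye is chosen by expected pain, and d the usual difference in pain between their two eyes. Steered patients contribute a shift of d and the others contribute zero on average, so the mean shift is f × d. Both inputs are assumed:

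- f = 0.25, d = 1 point: 0.25 × 1 = 0.25 point
- f = 0.50, d = 1 point: 0.50 × 1 = 0.50 point

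The shift favours CA if the calmer eye is put forward for CA. It is zero if the eye is fixed beforehand. Also, f cannot exceed the share of patients whose eye order is open, and the protocol does not give that share.

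**Step 4: effect on a paired test.** This is an illustration under no true difference, with a two-sided paired t-test at 5% and 20,000 simulated trials. The assumed inputs, none from the protocol, are an SD of the paired difference of 2.5 points and a foreseeable difference between eyes that is normal with mean 0 and SD τ. A share f of patients is steered toward CA in the calmer eye. The expected bias is f × τ × √(2/π), with √(2/π) = 0.798. For example, 0.5 × 1.0 × 0.798 = 0.40.

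| τ | f | Bias toward CA (points) | False-positive rate, 40 pairs | False-positive rate, one group of 10 |
|---|---|---|---|---|
| 1.0 | 0 | 0 | 5.0% | 5.0% |
| 0.5 | 0.25 | 0.10 | 5.6% | 5.1% |
| 1.0 | 0.25 | 0.20 | 8.1% | 5.9% |
| 1.0 | 0.50 | 0.40 | 16.6% | 7.3% |
| 1.5 | 0.50 | 0.60 | 33.0% | 11.0% |

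With the eye fixed first (f = 0) the rate stays at its nominal level.

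**Step 5: the two allocation statements side by side.** Section 2.3.2.1 lets the first eye receive either treatment. Section 1.4, read literally, gives the first eye one of the CA groups and the other eye SOC. Under that reading, choosing the first eye is choosing the CA eye, and no allocation need even be known. The point above takes the more favourable wording of section 2.3.2.1 and still stands.

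**The case against.** The strongest reply is that this is silence, not a wrong rule. A reader might infer from section 2.3.2.1 that staff pick the eye once they have seen the allocation, and that marking the brow is the moment when they do so. The protocol says neither. Marking is placed after consent, opens both the CA and the SOC procedures, and comes before the first mention of the randomised arm in the CA text. Marking before the allocation is opened fits the wording equally well, and in that order the problem disappears. A separate randomisation procedure may also deal with it.

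The scope is limited too. Section 1.4 says that most patients have their two injections within a 1–2 week period, and for them the treatment schedule may already decide which eye is due. On that wording same-visit patients are a minority, so f = 50% would need some two-visit patients to be steered as well. One earlier injection per patient need not reveal which eye hurts more. Steering that does not differ by CA group largely cancels when the groups are compared, and that comparison drives the choice of setpoint for the later phase in section 5.0.

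All of this limits the size and reach of the point. It does not remove it. The allocation rule is stated, it fixes order rather than eye, and nothing in the protocol closes the gap. Concealment of the sequence alone would not close it either, because the eye could still be named after the allocation is opened.

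**Conclusion.** The point holds as a weakness in the allocation rule: section 2.3.2.1 permits selection of the CA eye by unmasked staff, chiefly where both eyes are treated at one visit or booking is flexible. It does not hold as a claim that the protocol hands the choice to staff or that selection took place, and the document supports neither.

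The resulting bias in the CA minus SOC pain difference cannot be determined from the protocol. The 0.25 to 0.5 point range and the false-positive rates are illustrations that rest wholly on assumed values of f, d, τ and the SD of 2.5. They should not be quoted as the expected bias of this trial. The change is worth making because it costs almost nothing and the listed data could not repair such a bias afterwards.

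**What to change.** Amend section 2.3.2.1 as follows.

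- For every patient, same-visit or two-visit, the eye to be injected first (right or left) is recorded on the CRF after consent and before a concealed allocation is opened. Both parts are needed: naming the eye first protects nothing if the next assignment can be foreseen.
- The randomised assignment applies to that named eye. A later change, including one for clinical reasons, remains possible, is recorded as a deviation, and is analysed as randomised.
- If right or left is instead randomised directly for same-visit patients, the order of injection must also be fixed or randomised; otherwise the order of CA and SOC is left open.
- Sections 1.4 and 2.3.2.1 are reconciled, so that one statement says whether the first eye always receives CA or is randomised to CA or SOC.

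The cost is a few sentences, one CRF field and slightly less freedom to reorder eyes on the day. Visits and the sample size of 40 are unchanged.

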Patients receiving SOC undergo the risk of increased corneal keratopathy. In addition, patients receiving the SOC have an increased risk of post injection pain. The risk of mild ocular discomfort

with CA is mitigated by the use of proparacaine and also poses less risk to patients than topical lidocaine.

1.3.1 Primary Objective:

We plan to carry out a pilot study to collect preliminary data on the effectiveness of the cryoanesthesia (CA) device in minimizing the pain caused by intravitreal injections (IVT) and determine the most effective temperature and time of treatment. Specifically, we intend to record patients' subjective injection pain. The study will be carried out in patients receiving bilateral injections, and one eye will be anesthetized using the CA device, with the fellow eye receiving anesthesia via a topical lidocaine gel (SOC), a common method of providing anesthesia in current clinical practice.

1.3.2 Exploratory Objective(s):

We will measure injection preparation pain, 4-hr, and 24-hr post injection pain. Patients will rate ocular irritation immediately after injection as well as 4 and 24 hours after injection (1 – no irritation; 2 – mild irritation 3 – moderate irritation 4- marked irritation). Patients will rate visual function in the treated eye immediately after injection as well as 4 and 24 hours after injection (1 – no changes from baseline; 2 – mild blurring of vision 3 – moderate blurring of vision 4- marked blurring of vision). Physicians will record patients' objective response to intraocular needle penetration (1 – no pain/movement; 2 – mild pain/movement 3 – marked pain/movement with the injection). In addition, physicians will record the following common ocular side effects following IVT: subconjunctival hemorrhage (SCH), conjunctival hyperemia, and conjunctival injection. These will be assessed via a slit lamp examination performed within 30 minutes and 24 hours of the administration of the intravitreal injection. In addition, each eye will be assessed for other signs of anterior segment toxicity, including AC reaction or hypotony. Patients will be examined or receive a call 1 week after the injection to assess any adverse effects.

1.4 Anticipated duration of the clinical investigation:

[figure not shown]

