Physicians will record the following common ocular side effects following IVT: SCH, conjunctival hyperemia, and conjunctival injection. These will be assessed via a slit lamp examination performed within 30 minutes and 24 hours of the administration of the intravitreal injection. Patients will undergo an anterior segment ocular examination 1 day following their intravitreal injection, and the physician will again record the presence of SCH, conjunctival hyperemia, conjunctival injection, and corneal keratopathy. In addition, each eye will be assessed for other signs of anterior segment toxicity, including AC reaction or hypotony. Patients will be assessed by a phone call 1 week after injection in each eye for any adverse events.

Physicians will score ocular side effects of CA and SOC. We will conduct interim analysis every 12 weeks or following every 10th patient treated, whichever happens first, and will suspend the study if there appears to be significantly more ocular side effects following CA. For the reasons laid out

above (in the device description), we believe this device is minimal risk and has a very low probability of causing ocular side effects.

2.4 Study Outcome Evaluations:

2.4.1 Study Endpoints.

Primary Endpoint:

1. Injection pain - Pain rating on a visual analogue scale (1 to 10)

Exploratory Endpoints:

1. Injection preparation pain - Pain rating on a visual analogue scale, 1 to 10.
2. 4-hr post injection pain - Pain rating on a visual analogue scale, 1 to 10.
3. 24-hr post injection pain - Pain rating on a visual analogue scale, 1 to 10.
4. Physician recorded time from initiation of treatment to completion of the intravitreal injection.
5. Physician scored patient response to pain (1: no pain/movement; 2: mild pain/movement 3: marked pain/movement with the injection)
6. Physician scored ocular side effects within 30 minutes of administration of the intravitreal injection and 1 day following the injection (SCH, conjunctival hyperemia, conjunctival injection, and corneal keratopathy): 1: No ocular side effects; 2: mild ocular side effects (trace to 1+ SCH, conjunctival hyperemia, conjunctival injection, or corneal keratopathy; 3: Marked ocular side effects (SCH involving at least 25% of the ocular surface, 2-4+ conjunctival hyperemia or conjunctival injection, or 2-4+ corneal keratopathy). In addition, each eye will be assessed for other signs of anterior segment toxicity, including AC reaction or hypotony.

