In accordance with applicable policies of the University of Michigan Institutional Review Board (IRBMED), the investigator-sponsor will report, to the IRB, any observed or volunteered adverse effect that is determined to meet all of the following criteria: 1) *associated with the investigational device or, if applicable, other study treatment or diagnostic product(s)*; 2) *a serious adverse effect*; and 3) *an unexpected adverse effect*. Adverse event reports will be submitted to the IRB in accordance with the respective IRB procedures.

Applicable adverse effects will be reported to the IRB as soon as possible and, in no event, later than 10 calendar days following the investigator-sponsor's receipt of the respective information. Adverse effects which are 1) *associated with the investigational drug or, if applicable, other study treatment or diagnostic product(s)*; 2) *fatal or life-threatening*; and 3) *unexpected* will be reported to the IRB within 24 hours of the investigator-sponsor's receipt of the respective information.

Follow-up information to reported adverse effects will be submitted to the IRB as soon as the relevant information is available. If the results of the sponsor-investigator's follow-up investigation show that an adverse effect that was initially determined to not require reporting to the IRB does, in fact, meet the requirements for reporting; the investigator-sponsor will report the adverse effect to the IRB as soon as possible, but in no event later than 10 calendar days, after the determination was made.

3.1 Withdrawal of Subjects Due to Adverse Effects:

Patients will only have a single exposure to the device (10 to 20 seconds in length). Should a patient not tolerate the discomfort of the cold tip for the entire duration and be unable to receive full CA, that patient would be removed from the study.

If a patient withdraws from the study, the patient data will be destroyed. Another patient will be recruited to take their place, provided that the additional patient can be recruited and treated within the allotted study time frame.

3.2 Monitoring Plan:

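### Removing a patient who lacks the second injection, read with Section 3.1, can delete a completed first-eye record, and for refusals that loss can depend on the primary endpoint

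*Protocol*

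**What the plan says.** - **Removal.** Section 2.3.2.2 covers a patient who does not require, or refuses, "an injection in either eye, they will be removed from the study". It does not separate a patient with no treated eye from one whose first eye is finished.
- **Replacement.** The same section continues: "If patients withdraw from the study, we will plan to recruit additional patients to replace them".
- **Data.** Section 3.1 first removes a patient who cannot tolerate the cold tip, then states: "If a patient withdraws from the study, the patient data will be destroyed".
- **Timing.** Section 1.4 describes the usual interval as "1 eye at day 0, and the second eye by day 14". It also notes that some patients have both eyes injected at one visit.
- **Safety follow-up.** Section 2.3.3.2 has slit-lamp examinations within 30 minutes and at 24 hours, and then: "Patients will be assessed by a phone call 1 week after injection in each eye for any adverse events".
- **Use of the data.** Section 1.3.1 aims to "determine the most effective temperature and time of treatment". Section 5.0 carries one temperature and one time into a second phase after the first 40 patients are analysed. Section 2.3.3.2 also has an interim review of CA side effects, with possible suspension.
- **Expected frequency.** Section 2.3.2.2 states "Because IVT prevents blindness, the refusal of IVT is extremely rare" and "it is extremely rare for patient who have been determined to need IVT to have improvement in vision prior to IVT". It gives no figure for either.

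**The concern.** Injection pain is scored per eye. When the second injection falls due, the first eye can already have its primary endpoint, its 4-hour and 24-hour scores and its side-effect grades. The removal rule can therefore act after the outcome is known. For a refusal, the outcome may be the reason.

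A CA-first patient's CA score is informative about the device setting without a second eye. Removing that patient and recruiting another selects the setting's scores towards people who tolerated the first injection, most strongly in the most painful setting. Side-effect grades from a device-exposed eye could also drop out of the interim review. If the data are destroyed, no later analysis plan can recover them.

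**Working it through.** **1. What the text permits.** Section 2.3.2.2 goes from removal straight to replacing patients who withdraw. Section 3.1 goes from removal straight to destroying the data of a patient who withdraws. The protocol defines neither term and does not distinguish them. On the natural joint reading, a patient who refuses the second eye is removed and replaced, and the first-eye data are destroyed. Section 2.3.2.2 alone does not say this.

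**2. Sample size.** Four CA groups of 10 give 4 × 10 = 40, as stated in Section 2.2.2, with no dropout expected. One patient is a tenth of a group. As an illustration, replacing a score of 9 by a score of 4 moves the group mean by (9 − 4)/10 = 0.5 points.

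**3. How often.** The protocol gives no rate, so these are assumed. P(at least one) = 1 − (1 − r)^n.

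| Removal rate r | Expected of 40 | At least one of 40 | At least one in a group of 10 |
|---|---|---|---|
| 1% | 0.4 | 33% | 10% |
| 2.5% | 1 | 64% | 22% |
| 5% | 2 | 87% | 40% |
| 10% | 4 | 98% | 65% |

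**4. Effect on a setting's mean.** Simulation with all inputs assumed: rounded scores on 1-10, SD 2, SOC mean 4, CA mean 6, order randomised 1:1, refusal probability 10%, 20% or 40% after a first-eye score of 7 or more.
- CA-first patients lost: 4%, 8%, 16%.
- Half of patients are CA-first, so the chance that any one patient's CA score is lost is 0.5 × 4% = 2%, 4%, 8%.
- At least one CA score lost in 10: 1 − 0.98^10 = 18%; 1 − 0.96^10 = 34%; 1 − 0.92^10 = 57%.
- The retained CA mean is too low by about 0.04 to 0.17 points.
- The standard error of a 10-patient mean is 2/√10 = 0.63, so the bias is about 6% to 27% of one standard error (0.04/0.63 to 0.17/0.63).

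A second simulation used both true means 3.5, within-patient correlation 0.5, and refusal of 10-50% after a score of 6 or more. It removed 1.6-7.9% of patients, and the retained CA mean fell by about 0.04-0.19 points.

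**5. Effect on the paired difference.** In that second simulation with randomised order, CA minus SOC was essentially unbiased. With a true difference near 0.93 against CA (CA mean 4.5), retained patients showed 0.92 to 0.89. Section 2.3.2.1 randomises order, but one sentence in Section 1.4 can be read as CA always first. On that reading, with equal true pain, the difference shifts by about 0.03-0.14 points in favour of CA.

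**6. Follow-up.** If the second eye is due at day 7-14, the first eye's 24-hour examination is done and its 1-week call is done or due. Only a refusal at the same visit, or before the 1-week call, puts first-eye follow-up at risk.

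**The case against.** The strongest reply is that Section 2.3.2.2 says neither that the score is discarded nor that follow-up stops. The destruction sentence is in Section 3.1 and concerns a patient who withdraws. The 1-week call is tied to each injected eye, not to completing both. Which data enter which analysis is normally left to the analysis plan. This stands as far as it goes: both consequences come from reading sections together, and the follow-up consequence is narrow. An analysis plan cannot, however, bring back destroyed data.

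The design is also paired. If settings are compared on CA-minus-SOC differences, a lone first-eye score cannot contribute, and replacing an incomplete pair is ordinary. A reader might infer that the CA-SOC comparison is biased in favour of the device. With randomised order the calculations do not support that. The concern is confined to comparing CA scores between settings and to the side-effect record.

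A reader might also put the chance of loss in a 10-patient group at 23-66%. That counts SOC-first patients, who had no CA score to lose; 18-57% is the relevant range.

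Three further limits stand. The pain mechanism does not apply to patients who no longer require an injection. All patients have had an earlier injection, so injection pain is not new to them. The figures in step 4 use the most painful CA mean simulated, and smaller means give smaller effects. On the other side, the protocol's reason for expecting few refusals, that the treatment prevents blindness, does not address refusal after a painful injection under a study anaesthetic.

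**Conclusion.** The point holds in a limited form. As written, Sections 2.3.2.2 and 3.1 together permit irreversible loss of completed first-eye data, and for refusals that loss can depend on the primary endpoint. What is exposed is the choice of CA setting and the interim side-effect review.

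The expected bias is well below the sampling error of a 10-patient mean. It rests on assumed refusal rates, SD and means, and is near zero if refusal is as rare as the protocol states. It would be wrong to say that Section 2.3.2.2 itself discards the score or ends first-eye safety follow-up. The text is open to those outcomes but does not state them. The change is worth making because it is nearly free and the loss cannot be undone.

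**What to change.** In Section 2.3.2.2, state that for a patient who does not receive the second-eye injection:
- the patient leaves the paired CA-SOC comparison only;
- first-eye pain and side-effect data already collected are kept and reported and, if that eye had CA, enter the descriptive comparison of CA settings and the interim side-effect review;
- the 24-hour examination and 1-week call already scheduled for the treated eye are completed if the patient agrees;
- the reason for no second injection is recorded;
- a replacement may still be enrolled to restore the paired count.

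Reconcile removal in Section 2.3.2.2 with withdrawal and data destruction in Section 3.1, so that it is clear which patients the destruction sentence covers.

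The cost is a short text change with no added visits. The setting comparison may hold slightly more patients than the paired comparison. The change cannot supply a CA score for an SOC-first patient who refuses the CA eye, so recording the reason matters there too.
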